6.9.2 Recurrence-free Survival (RFS)

The recurrence-free survival (RFS) analysis objective is to ascertain whether the RFS time distribution for patients randomized to the experimental arm is consistent with longer RFS as compared to patients randomized to the control arm. All randomized patients will be included in the primary RFS analysis according to the randomized arm (intent-to-treat).

The following dataset variables are to be derived from the study database associated with a data cutoff date and used to perform the analysis of RFS associated with that data cutoff:

| Variable Name | Label | Definition |
|---------------|-------------------------------|--|
| strat | Randomization Stratum | A variable having a unique value for each possible combination of factors used in the stratified randomization scheme. |
| randd | Date of Randomization | Date patient is randomized. |
| expi | Experimental Arm Indicator | expi = 1 if patient is randomized to the experimental arm. expi = 0 if patient is randomized to the control arm. |
| rdi | Recurrence or Death Indicator | 
 • rdi = 1: The patient is known to have recurred or be dead without recurrence. The value of rdd (see below) is the date of recurrence or death. • rdi = 0: The patient is not known to have recurred and is not dead and is not known to have had a competing event. The value of rdd is the date the patient was last assessed for recurrence for a patient that has yet to experience, death, or a competing event (see below). rdi = 0 indicates that rdd is a censored date. • rdi = -1: The value of rdd is the date the patient was classified as having a competing event. rdi = -1 indicates that rdd is the date of a competing event. |
| rdd | Date of Recurrence or Death | The date of recurrence or death (rdi = 1) or the date last assessed for recurrence for a patient that has yet to experience death (rdi = 0) or the date of competing event (rdi = -1). See data imputation rules previously specified. |
| rdt | Time to Death | rdt = rdd - randd |

Imputation of missing dates will follow the rules previously specified. Competing events for RFS are “definite” lost to follow-up and withdrawal of consent for continued study participation. Both of these competing events are subject to revision for an individual patient with the passage of time.

The primary analysis will consist of executing two SAS procedures, a stratified log-rank test for the test of the hypothesis and a proportional hazard regression to estimate the hazard ratio and its 95% confidence interval.

```
proc lifetest;
  strata strat / group=expi test=logrank;
  time rdt*rdi(0,-1);
run;

proc phreg;
  class strat;
  strata strat;
  model rdt*rdi(0,-1)=expi / rl ties=exact;
run;
```

The significance of the logrank test will be assessed by referring the one-sided stratified logrank test P value to the significance criterion applicable to the analysis. The one-sided stratified logrank test P value, P_1 , is to be computed as follows from the hazard ratio estimate from the proportional hazard regression, HR, and the two-sided P value from stratified logrank test, P_2 : If $HR < 1$ then $P_1 = P_2/2$. If $HR \geq 1$ then $P_1 = 1 - P_2/2$.

Notes:

- These analyses must be stratified (3).
- When there are competing events then censoring competing events provides a between-arm test of the event of interest (4).

The RFS data will be plotted as either Kaplan-Meier or cumulative incidence distribution estimate depending on the amount of competing events. The cumulative incidence estimates and not the Kaplan-Meier estimates will be plotted if the percent of patients with competing events in either arm exceeds 10%. (When there are competing events then the Kaplan-Meier estimate is not an estimate of the probability free of event (5)).

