Key analyses may depend on the date of the first occurrence of an event associated with the endpoint. When the event has yet to occur the analysis will nonetheless require an analytical date be available for the analysis. These are known as censored or truncated dates. A censored date is the date of the most recent assessment for the event for a patient for which the event of interest has yet to occur and for which additional time may lead to observation of the event of interest. A truncated date is the date of a

competing event that precludes the observation of the event of interest. The distinction between designating an analytical date as censored or truncated will depend on the purpose of the analysis and will be designated for each analysis. For example, if death is the event of interest and a patient is still alive and being followed for the date of death then the date last known alive is a censored date, whereas the date a patient withdraws consent for continued follow-up of vital status (a competing event) is a truncated date. Please note that the nature of the competing event will dictate whether the competing event is permanent. For example, the date of death for a patient who has withdrawn consent may later become known passively from governmental death records.

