6.0 STATISTICAL ANALYSIS

Categorical variables will be summarized using counts and percentages. Percentages are based on the number of patients in the analysis set for whom there are non-missing data, unless otherwise specified.

Continuous variables, including change from baseline, will be summarized using descriptive statistics [n, mean, standard deviation (SD), minimum, median, maximum].

The rates of binary endpoints will be compared using a one-sided Pearson χ^2 test for unstratified analyses and Cochran-Mantel-Haenszel (CMH) test for stratified analyses. For the unstratified analyses, point estimates of the rates for each treatment arm and difference of the rates between treatment arms will be provided along with the corresponding 2-sided 95% confidence intervals using an exact method based on the F distribution and using a normal approximation for constructing a confidence interval for differences, respectively. For the stratified analyses, the relative risk ratio estimator will be used to contrast the treatment effects on the endpoint. Both a point estimate and a 2-sided 95% confidence interval will be calculated using a normal approximation.

Time-to-event endpoints will be summarized using the Kaplan-Meier method and displayed graphically when appropriate. Median event times and 2-sided 95% confidence interval for each median will be provided. Cox proportional hazard models will be used to explore the potential influences of the baseline stratification factor on time-to-event endpoints. The estimated hazard ratio and 2-sided 95% confidence interval will be provided.

Stratified analyses will be conducted controlling for the randomization stratification variables of disease state (IIB/IIC vs. IIIA vs. IIIB/IIIC).

Baseline is defined as the last data point prior to randomization in Part A or Part B of the study, unless otherwise stated. Baseline is defined as the last data point prior to dosing in the open-label extension of Part A, unless otherwise stated.

Patient data listings will include all enrolled or randomized patients as applicable to Part A, open-label extension of Part A, or Part B of the study. Listings will be presented by or include part of the study where appropriate, and be sorted by treatment group, site, patient number, and date (if applicable).

Statistical analyses will be carried out using SAS statistical analysis software version 9.1.3 or higher (SAS Institute, Inc., Cary, North Carolina, USA).

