24 APRIL 2019

Date

ADDENDUM #1

Section 1.0

Add the following text after the first paragraph:

Pre-Unblinding SAP modifications and extensions are specified based on realization of a need for clarification of the SAP, recognition of additional useful sensitivity and challenge analyses, a need to conform to precedents set by other similar studies, and a need to facilitate the understanding of results from this study in the context of other contemporary similar studies. The study remains blinded as this addendum is written. The primary statistical criteria are not changed as a result of this addendum.

The details of AESIs, concomitant medications of interest, treatment effect on non-melanoma and melanoma precursors are added as a separate document.

Note: This trial is double blind and therefore the following considerations apply to the time when the data can be unblinded. An unblinded analysis based on a January 1, 2019 cutoff and an April 25, 2019 soft lock will be prepared for a highly selected distribution. Immediately after release of the randomization file (consisting of two main items: patient identifier and actual assigned arm) this file will be sent to the consulting statistician. Following this transmission, and during the time when the final analysis SDTM datasets are being validated, the consulting statistician will use a merge of this randomization file with the blinded datasets already in possession of the consulting statistician to refine the study presentation slides working together with selected others. (The results are expected to be close to the final results.) The study presentation will be finalized after the validated SDTM datasets are sent to the consulting statistician.

Section 4.1

Delete the following sentence at the end of the first paragraph:

The primary efficacy analysis will be based on the ITT analysis.

Add the following text to the end of the first paragraph:

The ITT analysis set is to be considered as all patients randomized without regard to having initiated study intervention and free of pre-randomization findings of not meeting inclusion/exclusion criteria and not randomized in error, the existence of which must be discovered based on post-randomization review of data collected pre-randomization.

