When using SAS PROC LIFETEST quantile confidence intervals will be computed using the option CONFTYPE=LINEAR in order to invoke the Brookmeyer-Crowley method. When using PROC PHREG use the option TIES=EXACT.

Section 6.9.3.2

Add the following text as a bullet point after the first two bullet points in the first paragraph:

An RFS sensitivity analysis with the event defined as the date of recurrence or if there is no observed recurrence then date of death up to 120 days since last recurrence assessment. Censoring for this analysis will be the date of last recurrence assessment.

[End of Addendum #1]

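### SAP 6.9.2 would switch the RFS figure to cumulative incidence because of dropout; if triggered under non-informative dropout, the figure understates event risk in both arms and departs from the reported Kaplan-Meier median

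*SAP*

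**What the plan says.** SAP 6.9.2 counts recurrence or death as the RFS event. The only competing events it lists are definite "lost to follow-up and withdrawal of consent for continued study participation". It adds: "Both of these competing events are subject to revision for an individual patient with the passage of time". SAP 4.6 makes the same point by example: "the date of death for a patient who has withdrawn consent may later become known passively from governmental death records".

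The model SAS calls in 6.9.2 put codes 0 (censored) and -1 (competing event) in one censoring list, for both the logrank test and the Cox model. A note explains that "When there are competing events then censoring competing events provides a between-arm test of the event of interest". The plotting rule follows: "cumulative incidence estimates and not the Kaplan-Meier estimates will be plotted if the percent of patients with competing events in either arm exceeds 10" per cent. The stated reason is that Kaplan-Meier does not estimate the event-free probability when competing events exist.

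Elsewhere the summary is Kaplan-Meier. SAP 6.0 says "Median event times and 2-sided 95% confidence interval for each median will be provided", and Addendum 1, in its changes to 6.9.2, says "quantile confidence intervals will be computed using the option CONFTYPE=LINEAR in order to invoke the Brookmeyer-Crowley method". Addendum 1 replaces the definitions of rdi and rdd but leaves the competing-event sentence and the 10% rule in place.

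**The concern.** Cumulative incidence is the right display when a competing event removes the patient's chance of the event, as death without recurrence does for time to recurrence. Here death is inside the endpoint. Only dropout is left, and a patient who drops out can still recur or die, as 6.9.2 and 4.6 acknowledge.

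With dropout as the competing cause, the curve estimates the probability of an event observed before dropout. That lies at or below 1 minus Kaplan-Meier. If dropout is non-informative, the figure shows too little risk in each arm, and it rests on a different treatment of dropouts from the test, the hazard ratio and the median. RFS is the sole primary endpoint of Part B1 and one of two in Part B2, so this figure will be looked at closely. Either arm alone can trigger the switch.

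**Working it through.** **Inputs from the documents.** SAP 5.2.1 gives the control arm: stage II 30.9%, hazard 0.154 per year; IIIA 30.4%, 0.198; IIIB/C 38.7%, 0.409. It also gives the vaccine effect: hazard ratio 1 to month 1, falling linearly to 0.625 over 3 months, then 0.625 (form in Appendix 3). B1 accrues 325 patients in 1.5 years, with analysis at 3.21 years. B2 accrues 800 in 3 years, with analysis at 3.93 years (5.2.2). Addendum 1 plans "An unblinded analysis based on a January 1, 2019 cutoff and an April 25, 2019 soft lock". It does not name the part; I take it as B1, about 4.0 years after the January 2015 start.

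**Assumption.** Dropout is independent with constant rate w. The documents give no rate, and Appendix 3 plans with competing events absent or negligible.

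**Model check.** The 10% rule has no derived figure to reproduce. Simulating the B1 design (126 events, 2:1, stratified one-sided logrank at 0.10) gave power of 81.5-81.7% against the SAP's 80.5%. Mean analysis time was 3.3-3.5 years against 3.21.

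**Formulas.** With stage proportions p, hazard h and cumulative hazard H:
- Kaplan-Meier risk at t = 1 - Σ p·exp(-H(t))
- Plotted cumulative incidence = Σ p·∫ h(u)·exp(-H(u) - wu) du, from 0 to t. For placebo (constant hazard λ) each term is p·λ/(λ+w)·[1 - exp(-(λ+w)t)]
- Share dropped out = Σ p·∫ w·exp(-H(u) - wu) du, averaged over entry times

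**Placebo at 3 years, w = 0.05.**
- Kaplan-Meier: 0.309×0.3700 + 0.304×0.4479 + 0.387×0.7068 = 0.524
- Cumulative incidence: 0.309×0.3455 + 0.304×0.4190 + 0.387×0.6662 = 0.492

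**Dropout rate at which either arm passes 10%** (uniform entry / 1-year linear ramp):

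| Analysis | Rate per year |
|---|---|
| B1 at 3.21 y | 5.4% / 5.8% |
| B1 at 4.0 y | 4.3% / 4.5% |
| B2 at 3.93 y | 5.5% / 6.0% |

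At 5% per year, B1 at 4.0 years would have 9.9-10.3% of placebo and 11.0-11.5% of vaccine patients dropped out.

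**Plotted against Kaplan-Meier event risk:**

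| w, time | Placebo | Vaccine | Arm gap (points) |
|---|---|---|---|
| 5%/y, 2 y | 38.0% vs 39.8% | 27.7% vs 29.0% | 10.3 vs 10.8 |
| 5%/y, 3 y | 49.2% vs 52.4% | 36.7% vs 39.1% | 12.5 vs 13.3 |
| 6%/y, 3 y | 48.6% vs 52.4% | 36.2% vs 39.1% | 12.4 vs 13.3 |

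The placebo curve reaches 50% at 3.09 years (5%/y) or 3.16 years (6%/y); the Kaplan-Meier median is 2.79. The modelled vaccine median, 4.33 years, lies beyond the roughly 4.0 years of maximum follow-up. The 3-year values are relevant at the 2019 cutoff: SAP 5.2.1 reports 212 patients accrued in 2015, so 212/325 = 65% could have 3 years of follow-up.

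A simulation of 400,000 patients per arm (5%/y, 4.0 years) agreed at 3 years: cumulative incidence 49.2% and 36.6%, event-free by Kaplan-Meier 47.6% and 61.0%.

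**Unequal dropout.** Give both arms the placebo hazards, with 5% lost by year 3 in one and 15% in the other. The plotted 3-year risks are 50.8% and 47.5%: a spurious 3.3-point advantage for the arm with more loss. Under the planned effect, the plotted gap is 15.1 points if vaccine loses 15% and placebo 5%, and 9.5 points if reversed, against 13.3 by Kaplan-Meier.

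**The case against.** - **It touches only a figure.** This stands. The median is also reported as a number, and Kaplan-Meier plots by arm and factor are planned for RFS (6.9.3.1, applied through 6.9.3.2).
- **It may never be triggered.** This stands. Besides the missing dropout rate, the ascertainment rules in Addendum 1 describe only events and censoring, with no competing-event code. Whether any patient would still count towards the 10% is unclear.
- **Dropout fits the SAP's own definition.** SAP 4.6 calls a competing event one that prevents the event of interest from being observed. A reader might infer that the passages contradict each other; they do not. The fault is the estimator built on that definition.
- **Kaplan-Meier is also biased if dropout is informative.** True, but cumulative incidence does not repair this, because it treats dropouts as unable to recur or die.
- **Removing the rule could do harm.** This stands and shapes the fix. SAP 6.10.1 analyses time to locoregional and time to distant recurrence as for RFS, so they inherit the SAP's only cumulative-incidence provision. For them, death is a true competing risk.

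**Conclusion.** The estimator is wrong for RFS, but the error is one of presentation and of low severity. Just above the trigger, the figure would understate risk by 1.8 points (placebo) and 1.3 points (vaccine) at 2 years, and by 3.2 and 2.4 points at 3 years. Within follow-up, the mismatch with the median concerns placebo only. These sizes rest on the SAP's planning hazards and on assumed independent dropout.

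Two stronger readings are not supported. One is that the primary RFS result is biased: the tests already censor dropouts, so the P value, hazard ratio and event count are the same with or without the rule. The other is that the rule flatters the vaccine. With equal dropout the arm gap shrinks slightly and the ratio of event risks stays at about 0.73 (2 years) and 0.75 (3 years). A false or enlarged difference needs unequal dropout, in either direction, and nothing in the documents says that will occur.

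**What to change.** In SAP 6.9.2, for RFS:
1. Delete the 10% switch and the competing-event sentence. Always plot Kaplan-Meier, with dropouts censored as in the primary analysis.
2. Report loss to follow-up and withdrawal of consent by arm with the figure, so that readers can judge whether non-informative dropout is plausible.
3. State that rdi takes only 1 (event) and 0 (censored), and drop -1 from the RFS SAS calls. Do not restore the coding that Addendum 1 replaced: it would bring the competing-event category back, and a record coded -1 would count as an event once -1 left the censoring list.

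In SAP 6.10.1, state separately that time to locoregional and time to distant recurrence are plotted by cumulative incidence, with death without that recurrence as the competing event and dropout censored.

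The cost is SAP wording and the plots for those two endpoints. No new data are needed, and the RFS Kaplan-Meier estimates already come from the planned LIFETEST call.

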6.9.3 Sensitivity Analyses of Efficacy Endpoints

6.9.3.1 Sensitivity Analyses of Overall Survival (OS)

The following sensitivity analyses for OS will be performed:

- The primary OS analysis will be performed using the ATAS.
- Deaths that occur after the cutoff will not be censored.
- Clinical site homogeneity will be assessed by testing the arm by site or site class interaction. This open-ended exploration will assess homogeneity across sites using the following clumping of sites: Clinical sites with patients fewer than K patients in either arm will be pooled into a single pseudo clinical site. K will be varied in the range of 2 to 8. Classes of clinical sites will be analyzed according to characteristics such as region, type of facility, or homogeneity of medical practice for treating melanoma.
- The proportional hazard regression (PHR) will be re-run without the strata statement and with the treatment arm by stratum interaction term added to the model statement in order to assess the interaction between the treatment arms and the disease states at randomization.
- Effect modifier analyses will be performed for base attributes and particularly putatively prognostic factors, including those explored previously in the literature as well as those hypothesized to be predictive in the context of this study. These are listed subsequently. Effect modification will be assessed one factor at a time in stratified PHR models. Each factor will be analyzed as either a natural dichotomy, a dichotomized ordered categorical with cutpoint chosen based on biologic considerations, or a continuous variable dichotomized at the overall median, and possibly tertiles, quartiles or quintiles. A separate hazard ratio estimate for arm and its 95% confidence interval will be computed for each level of the categorical attribute

using contrast statements in SAS PROC PHREG. Kaplan-Meier estimates of combinations of arm by factor will be plotted on.

- Proportional hazard regression models with multiple added prognostic covariates will be estimated. The covariates to be added will include those explored previously in the literature as well as those hypothesized to be predictive in the context of this study. Interactions will also be explored for contribution to the model.

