5.2.1 Part B1

Part B1 is a two-arm comparison of the efficacy of the experimental arm where the intended intervention is the experimental vaccine (Arm V) against a control arm where the intended intervention is placebo (Arm P). The primary analysis is based on recurrence-free survival (RFS). This analysis is based on the original hypothesized RFS hazard ratio and assumed control arm RFS distribution. The analysis is specified to be an intent-to-treat comparison of Arm V to Arm P using the stratified logrank

test. The major change brought about as a result of splitting the original Part B into Parts B1 and B2 is to implement a relaxed the type I error probability for Part B1.

The following table is used to specify Arm P (control arm) reference data by stage strata. The original specification of proportions expected came from a review of the articles reporting outcome from recent trials in melanoma. The empirical proportions come from trial experience to date. The stratum-specific empirical proportions are used to compute the trial size and timing as described subsequently.

| Stage | Original Proportions (%) | Empirical Proportions (%) | RFS median (y) | RFS rate |
|--------|--------------------------|---------------------------|----------------|----------|
| II | 30 | 30.9 | 4.5 | 0.154 |
| IIIA | 36 | 30.4 | 3.5 | 0.198 |
| IIIB/C | 34 | 38.7 | 1.7 | 0.409 |

The best single source of effect size data is reference (1). This article reports data from a small (38 patient) double-blind randomized trial of a similar vaccine. The estimated medians for RFS are 0.6 and 1.6 years for placebo and vaccine, respectively, providing a crude hazard ratio estimate of 0.38 ($= 0.6/1.6$). Therefore, Polynoma's hypothesized RFS hazard ratio is 0.625 for RFS, corresponding to a 37.5% smaller RFS hazard rate for Arm V patients. This hypothesized hazard ratio is consistent with a clinically meaningful effect, especially when weighed against the expected low adverse event profile.

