5.2.2 Part B2

Conditional on the results from the RFS analysis from Part B1, a follow-on phase of the trial is planned that is designated as Part B2. The analysis of the B2 RFS will be supportive to the BLA to be submitted. Patients will be randomized with equal probability to a control arm for which the planned intervention is placebo, or to an experimental arm, for which the planned intervention is vaccine.

Part B2 of the trial will have co-primary endpoints of RFS followed by survival with an overall one-sided alpha of 0.025. The significance level to be used for RFS is specified to be one-sided 0.02, and the significance level to be used for the subsequent survival analysis is specified to be 0.005. (Note: The survival data from Part B1 will not be included in the analysis of survival for Part B2.) The trial is planned with power of 90% for RFS and 80% for survival.

The Part B2 trial is planned with the specific alternative RFS HR = 0.625, and the specific alternative survival HR = 0.6667 as was originally planned.

The Part B2 RFS analysis is planned using the same delayed effect specifications as were used to plan the Part B1 analysis and accrual of 800 patients in 3 years.

Simulations with 10,000 replications find a requirement for 310 RFS events and the last of these events is projected to occur 3.93 years following the start of accrual. The simulation estimate of alpha is 0.0126, the simulation estimate of power is 90.2%, and the critical RFS hazard ratio region is estimated to be ≤ 0.791 , corresponding roughly to a 26% or longer median RFS.

An interim futility and efficacy survival analysis will be performed at the time of the Part B2 RFS analysis; the final survival analysis will be done at 432 deaths. The significance levels to be used for the interim and final survival analyses are specified to be equal (not based on O'Brien-Fleming bounds) with protection of the overall one-sided 0.005 in the survival efficacy analyses. The decision to use equal significance levels at interim and final is based on increasing the chances of finding early evidence of survival efficacy.

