The exact number of deaths at the time of the RFS analysis cannot be known at this time there will be an appropriate adjustment in the final efficacy significance level to be used based on the actual events at the time of the survival analysis. Assume the number of deaths at the time of the final RFS analysis is D. The information time (stated as a proportion) for the survival analysis to be done at the RFS analysis time will therefore be D/432. This proportional information time will be used to compute bounds with equal significance levels using the power method. The software suggested is SAS PROC SEQDESIGN, but other options are available.

It is projected that at the time of the analysis of RFS there will be 157 deaths in Part B2, with an information time of 36% (157 of 432). Based on the having equal significance levels for the interim and final survival analyses it is computed using SAS PROC SEQDESIGN with the power method rho specified to be 0.0003 gives significance levels of 0.002625. The survival futility analysis will be done using significance level 0.0001 and the methodology to be used for the futility analysis is described in the [Appendix “Futility Analysis.”](#)

The statistical operating characteristics for the Part B2 survival endpoint assessment requires 432 deaths and the last of these events is projected to occur 13 years following the start of accrual. The simulation estimate of alpha is 0.0030, the simulation estimate of power is 80.2%, and the critical survival hazard ratio region is estimated to be ≤ 0.764 , corresponding roughly to 31% or longer experimental arm median survival.

For the Part B2 futility survival assessment, the probability of declaring futility is estimated to be 10.7% when $HR = 1$ with critical hazard region of ≥ 1.20 , corresponding roughly to a 17% shorter experimental arm median survival. The probability of falsely declaring superiority when $HR = 1$ is 0.08%.

For the superiority interim assessment, the probability of declaring superiority when $HR = 0.6667$ is estimated to be 21.1% with critical hazard region of ≤ 0.637 , corresponding roughly to a 57% longer experimental arm median survival. The probability of falsely declaring superiority under the null hypothesis is 0.22%.

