Imputation of missing dates will follow the rules previously specified. Competing events for death are “definite” lost to follow-up and withdrawal of consent for continued vital status assessments. While both of these competing events are subject to revision for an individual patient with the passage of time it is considered unlikely. The primary analysis will consist of executing two SAS procedures, a stratified logrank test for the test of the hypothesis and a proportional hazard regression to estimate the hazard ratio and its 95% confidence interval. Model SAS code for these two procedures is as follows:

```
proc lifetest;
  strata strat / group=expi test=logrank;
  time dt*di(0,-1);
run;

proc phreg;
  class strat;
  strata strat;
  model dt*di(0,-1)=expi / rl ties=exact;
run;
```

The significance of the logrank test will be assessed in Part B2 by referring the one-sided stratified logrank test P value to the significance criterion applicable to the analysis. The one-sided stratified logrank test P value, P_1 , is to be computed as follows from the hazard ratio estimate from the proportional hazard regression, HR, and the two-sided P value from stratified logrank test, P_2 : If $HR < 1$ then $P_1 = P_2/2$. If $HR \geq 1$ then $P_1 = 1 - P_2/2$. The analysis of survival for Part B1 will be descriptive and use the same methods, with a focus on confidence intervals of estimates.

Notes:

- These analyses must be stratified (3).

- When there are competing events then censoring competing events provides a between-arm test of the event of interest (4).

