6.9.3.2 Sensitivity Analyses of Recurrence-free Survival (RFS)

The following sensitivity analyses for RFS will be performed:

- The same sensitivity analyses specified for as sensitivity analyses of survival will be done for RFS.
- Sensitivity analyses of alternative coding of the date of recurrences and censoring will be performed. These analyses will follow the suggestions in the FDA Guidance for Industry Clinical Trial Endpoints for the Approval of Cancer Drugs and Biologics, May 2007 ([Appendix 3](#)).

All secondary efficacy analyses and sensitivity analyses will be presented by randomized treatment, based on the ITT analysis set, unless otherwise specified.

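### The arm-by-stage sensitivity Cox model drops STRATA and names no stage main effect; coded literally, it reports stage prognosis as treatment interaction

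*SAP*

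**What the plan says.** The template Cox code in SAP 6.9.1 (OS) has the model line "model dt*di(0,-1)=expi / rl ties=exact", and that in 6.9.2 (RFS) has "model rdt*rdi(0,-1)=expi / rl ties=exact". In both, `expi` is the only covariate. It is a numeric 0/1 variable, because the CLASS statement lists only `strat`. Stage reaches the model only through `strata strat`.

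One sensitivity bullet in SAP 6.9.3.1 asks for this regression to be "re-run without the strata statement and with the treatment arm by stratum interaction term added to the model statement". Its stated aim is to examine whether the treatment effect differs by disease state at randomization. No stage main effect is mentioned, no code is given, and no test level is set. SAP 6.9.3.2 extends the bullet: "The same sensitivity analyses specified for as sensitivity analyses of survival will be done for RFS".

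Addendum #1 returns to the `strat` variable (its source is the IVRS) and to the procedure options ("When using PROC PHREG use the option TIES=EXACT"). It leaves the interaction bullet as it was.

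**The concern.** The instruction is an edit to given code. It removes the only stage control and names one replacement term. Carried out literally, it gives `expi expi*strat`, in which placebo patients of all stages share one hazard. The vaccine arm has a separate hazard for each stage, so the ordinary prognostic difference between stages is attributed to treatment.

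The SAP's own planning table makes that difference large. The control RFS rate is 0.154 per year in stage II and 0.198 in IIIA, and the last row reads "IIIB/C | 34 | 38.7 | 1.7 | 0.409". The ratio of highest to lowest is 0.409/0.154 = 2.66.

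This is the only bullet that names a test of arm against the three randomization strata, and the error has a misleading direction. A vaccine that worked equally in every stage would look strong in stage II and useless in IIIB/C. One that did nothing would look helpful in II and harmful in IIIB/C. Part B1 is meant to inform whether Part B2 is justified, so such a table could mislead its readers, although the SAP attaches no decision rule to it.

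**Working it through.** **1. The literal model.** For arm x (0 or 1) and stage s it is h(t | x, s) = h0(t)·exp(βx + γ_s·x). When x = 0 every term vanishes, so placebo has the single hazard h0 in all stages. In the vaccine arm the fitted arm hazard ratio for stage s is roughly HR·λ_s / λ_pooled, which varies with λ_s even when HR is the same in every stage.

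**2. Hand check (RFS; rates and empirical stage mix from SAP 5.2.1).** The mix-weighted control rate is 0.309×0.154 + 0.304×0.198 + 0.387×0.409 = 0.0476 + 0.0602 + 0.1583 = 0.266. With HR 0.625 in every stage:
- II: 0.625×0.154/0.266 = 0.36
- IIIA: 0.625×0.198/0.266 = 0.47
- IIIB/C: 0.625×0.409/0.266 = 0.96

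The simulated values in step 4 are slightly higher (0.38, 0.49, 1.02). They correspond to a pooled rate of about 0.25, for example 0.625×0.154/0.382 = 0.252, because high-risk patients leave the risk set first.

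**3. Check of the simulated design against the plan.** The SAP states no figure for the interaction model, so its design power was reproduced instead. Inputs were the SAP stage mix and rates, the 1-month plus 3-month delay to HR 0.625, and uniform accrual; there were 4,000 replicates.
- B1 (325 patients, 2:1, 126 events, one-sided 0.10): 81.4% stratified and 80.1% unstratified, against 80.5% stated.
- B2 (800 patients, 1:1, 310 events, one-sided 0.02): 92.5% stratified and 91.2% unstratified, against 90.2% stated.

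B1 agrees closely; in B2 the stratified figure is 2.3 points above the stated one.

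**4. Rejection of the 2-df interaction test at 5%, RFS, no true interaction.** The 5% level is an assumption. Two independent sets of simulations were run: Wald tests (4,000 trials per B1 row, 2,000 per B2 row) and likelihood-ratio (LR) tests (2,000 per row). Entries are percentages.

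| Size | True HR, all stages | Literal, Wald | Literal, LR | STRATA kept, Wald | Main effect added, Wald | Main effect added, LR |
|---|---|---|---|---|---|---|
| B1 | 1 | 94.4 | 94.5 | 3.6 | 3.9 | 6.1 |
| B1 | 0.625 | 90.9 | 92.0 | 4.0 | 4.0 | 5.5 |
| B1 | 0.625, delayed | 91.4 | – | 3.9 | 4.0 | – |
| B2 | 1 | 100.0 | 99.9 | 5.2 | 5.3 | 5.0 |
| B2 | 0.625 | 99.5 | 98.9 | 5.1 | 5.2 | 5.8 |
| B2 | 0.625, delayed | 99.7 | – | 5.0 | 4.6 | – |

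Median fitted arm hazard ratios from the literal model at B1 size (II, IIIA, IIIB/C) were 0.61, 0.77, 1.60 when the truth was 1 throughout, and 0.38, 0.49, 1.02 when it was 0.625 throughout. With the stage main effect added, the latter became 0.62, 0.62, 0.62.

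**5. Smaller stage gradient (RFS, B1 size, 2,000 trials each).** Literal-model rejection at HR 1 and HR 0.625 was 74.4% and 67.8% at a 2.08-fold spread, 38.6% and 33.8% at 1.63-fold, and 10.8% and 9.4% at 1.25-fold. Correct models stayed at 4.2–5.1%.

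**6. OS (B2, 2,000 trials each).** The SAP plans "the specific alternative survival HR = 0.6667 as was originally planned" and says the endpoint "requires 432 deaths and the last of these events is projected to occur 13 years following the start of accrual", but gives no stage-specific death rates. The stage spread is therefore an assumption, shown as a range. Survival was taken as exponential, with its level set to give 432 deaths at 13.0 years under HR 0.6667.

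| Assumed spread | Literal, HR 0.6667 | Literal, HR 1 |
|---|---|---|
| 1.25-fold | 20.2% | 24.4% |
| 1.5-fold | 56.7% | 63.1% |
| 2.0-fold | 96.4% | 98.6% |
| 2.66-fold | over 99% | over 99% |

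Correct models rejected in 4.5–5.3%.

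**The case against.** The strongest reply is that the SAP does not prescribe this model. The bullet is prose, and its purpose is to assess interaction, which a model lacking the stage main effect cannot do. Dropping STRATA is the usual step when stage moves into the MODEL statement. SAP 6.0 plans Cox models that explore the influence of the stratification factor, and both templates already declare `strat` in CLASS. A programmer following the hierarchy convention would add the main effect unprompted.

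Much of this stands. It makes the full-model reading plausible, and it means every rejection rate above is conditional on literal coding. It does not supply the missing term: the sentence in SAP 6.0 is general, and a CLASS declaration serves `expi*strat` just as well.

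A second reply is that the next bullet of 6.9.3.1 estimates effect modification in stratified models, with stage among the listed attributes, so a false interaction would visibly conflict with those estimates. That is partly right. However, the stage attribute in 6.9.4 has two levels (IIB against III), so no specified analysis checks the three-stratum result. The open-ended multi-covariate models might, but they are not specified.

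A third reply is that the bullet carries no test level and no decision rule. That is correct, and it limits the consequence.

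**Conclusion.** The wording is deficient and should be corrected, but the point is narrow. If the template is edited literally, then for RFS under the SAP's stage rates and mix a false stage interaction is reported in about 91–95% of B1-size and about 99% or more of B2-size trials. A uniform hazard ratio of 0.625 is displayed as about 0.38/0.49/1.02. These figures assume a 5% 2-df test, exponential times within stage in placebo, uniform accrual and the planned event counts. They fall quickly with a flatter stage gradient.

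Three stronger inferences are not supported:
- A reader might infer that the planned stage analysis will be wrong. It will be wrong only if coded literally, and many statisticians would not do so.
- A reader might infer that the OS test would usually give a false positive. The SAP has no stage-specific death rates, and at a 1.25-fold spread rejection is only 20–24%.
- A reader might infer that the trial's main result is at risk. The primary stratified logrank test and the stratified hazard ratio do not use this model.

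**What to change.** Replace the bullet in SAP 6.9.3.1, and so for RFS through 6.9.3.2, with:

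> The stratified PHR (STRATA strat retained) will be re-run with expi*strat added to the MODEL statement; the 2-df interaction test and the arm HR for IIB/IIC, IIIA and IIIB/IIIC will be reported.

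State the test level as well. If the authors prefer to drop STRATA, fit `expi strat expi*strat` and note that this also assumes proportional hazards between stages, which the STRATA version does not. The choice matters little in the settings tried. With non-proportional (Weibull) stage baselines at the SAP medians and HR 0.625 in every stage, rejection was 4.6–5.6% with STRATA kept and 4.9–6.0% with the main effect, against 92.0–99.5% for the literal model.

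The cost is one sentence of SAP text, with no new data and no change to the primary analysis.
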